3.6 Follow-up and Events of Interest

Patients included in the study will be followed from the date of diagnosis of T2D until the date of the last available visit.

During the follow-up, for all included patients, the year of onset of the first cancer occurring after the diagnosis of diabetes and the type of cancer will be recorded. From this information, it will be possible to calculate the time elapsed between the diagnosis of diabetes and the onset of the tumor (measured in years).

For patients who have developed cancer, the following will also be recorded:

- Cancer recurrence (year of recurrence onset)
- Diagnosis of a second cancer unrelated to the primary cancer (year of onset, type of cancer)

Cancer diagnosis will be identified through the extraction system from the Smart Digital Clinic electronic medical record (Meteda Srl), using relevant keywords in the cancer domain, identified in the medical history section. The keywords will include: metastasis, adenocarcinoma, carcinoma, neoplasm, secondary, sarcoma, cancer, adenoma, lymphoma, leukemia, glioma, glioblastoma, basal cell carcinoma, squamous cell carcinoma, melanoma, mesothelioma, chordoma, anaplastic, differentiated, undifferentiated, meningioma, multiple myeloma, small cell carcinoma, thymoma, craniopharyngioma, neuroendocrine, LH, NHL, K, GIST, HCC, and NET.

SCDU di Endocrinologia

AOU Maggiore della Carità, [name]
[contact] (Reparto); [contact]
[contact]

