Finally, regarding cancer, treatment will be categorized into three classes: chemotherapy, surgery, and radiotherapy. Additionally, cancer types will be divided to ensure greater homogeneity among groups, including the nervous system, head and neck, thorax, gastrointestinal, gynecological, urinary tract, male genital system, skin, blood, breast, soft tissues, endocrine glands, and neuroendocrine cancers.

Such information will be collected at the diabetes diagnosis visit and the last visit before cancer onset for subjects experiencing the event, and at the last available visit for the remaining subjects.

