3.8 Sample Size

Assuming a type I error of 0.05, a power of 80%, a prevalence of subjects with high glycated hemoglobin levels of 13%, and a correlation between covariates in the model of 0.1, it will be necessary to identify 779 cancer cases to highlight a Hazard ratio of 1.2 for the association between glycated hemoglobin and cancer onset.

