3.9 Statistical Analysis

Descriptive statistics will be calculated to summarize patient information.

Categorical variables will be reported as absolute frequencies and percentages, while numerical variables will be reported as mean and standard deviation or median (Q1-Q3) if not distributed according to a normal random variable according to the Shapiro-Wilk test and observation of the QQ plot.

SCDU di Endocrinologia

AOU Maggiore della Carità, [name]
[contact] (Reparto); [contact]
[contact]

Univariate and multivariate Cox proportional hazards regression models will be used to estimate hazard ratios (HRs) and corresponding 95% confidence intervals (95% CI) for the association between some risk factors, including particularly glycemic level, and cancer onset. The stepwise method will be used to select variables to include in the model. For this analysis, time to event will be calculated as the number of years between cancer onset and diabetes diagnosis for subjects who develop the cancer, and as the number of years between the last available visit and the date of diabetes diagnosis. The possibility of conducting an analysis separately for cancer type or considering specific cancer types based on the number of observed events will be evaluated. The same models will be used to estimate the association with the risk of recurrence, second cancer, or both in patients who have developed cancer. In this case, time to event will be calculated considering the difference in years between recurrence onset, second cancer, or last visit and the onset of the first cancer.

Linear regression models will be used to evaluate the relationship between variables measured at diagnosis and time to cancer onset. In case the assumptions of the linear model are not met (normality of residuals and homoscedasticity), the Spearman correlation coefficient will be calculated to measure the correlation between numerical variables and time to tumor onset, while the Mann-Whitney or Kruskall-Wallis tests will be used when variables measured at baseline are categorical.

The significance level will be set at 0.05, and all tests performed will be two-tailed. Finally, the analyses will be conducted using SAS software (version 9.4; SAS Institute, Cary, NC, USA).

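### A basal or squamous cell skin carcinoma counts as the first cancer, ends primary follow-up and moves any later cancer to a secondary analysis; this may dilute the HbA1c and BMI associations, and no analysis without these lesions is planned.

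*Combined protocol and SAP*

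**What the plan says.** Section 3.6 (Follow-up and Events of Interest) defines the event without restricting tumor type: "the year of onset of the first cancer occurring after the diagnosis of diabetes and the type of cancer will be recorded". Cases are found by keyword search of the medical history, and the keywords include "basal cell carcinoma, squamous cell carcinoma, melanoma". For patients with a cancer, recurrence and a second, unrelated cancer are also recorded.

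Section 3.7 (Data Collection) groups the cancers, and skin is one undivided class in that list: "male genital system, skin, blood, breast, soft tissues". The purpose given for the grouping is homogeneity within groups. The same section takes the later covariate values at the last visit before cancer onset for patients with the event, and at the last available visit for the others.

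Section 3.9 (Statistical Analysis) measures primary time from diabetes diagnosis to cancer onset. Recurrence and second cancer are analysed with the clock starting at the first cancer. Analysis by cancer type is something to be considered once event counts are known. No section excludes basal or squamous cell skin carcinoma from the event, or commits to an analysis without it.

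**The concern.** A single skin lesion has several consequences under these rules. Take an invented patient with a basal cell carcinoma in year 3 after diabetes diagnosis and a colon cancer in year 10.

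- In the primary Cox model the patient is an event at year 3, and the colon cancer does not enter.
- The T1 values of HbA1c, BMI and treatment are those before year 3.
- The colon cancer appears only in the second-cancer model, at 10 - 3 = 7 years on a clock started by the skin lesion.
- In the regression of time to cancer onset (secondary objective 3), the outcome is 3 years.

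At stake is what the primary hazard ratios describe. If these lesions are less strongly related to HbA1c or BMI than other cancers are, mixing them in pulls the estimates toward 1 and costs power. Some follow-up in which other cancers occur is also removed from the primary analysis. The recurrence and second-cancer results would partly describe what follows a skin lesion.

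**Working it through.** **1. The plan's event count.** Section 3.8 gives the inputs: "Assuming a type I error of 0.05, a power of 80"%, "a prevalence of subjects with high glycated hemoglobin levels of 13"%, "a correlation between covariates in the model of 0.1", and 779 cases "to highlight a Hazard ratio of 1.2". Section 3.9 adds "all tests performed will be two-tailed". For a binary covariate in a Cox model (Schoenfeld), with variance inflation for the correlation:

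events = (1.960 + 0.842)² / [0.13 × 0.87 × (ln 1.2)²] / (1 - 0.1²) = 2,088 / 0.99 = 2,109.

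The stated 779 is not reproduced; the same formula returns 779 at a hazard ratio of 1.35. That mismatch is a separate matter and does not affect this point. Power is shown below for both counts.

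**2. Observed hazard ratio.** Two inputs are not in the documents and are assumed: the share s of basal/squamous skin carcinoma among first cancers in the low-HbA1c group, taken as 10-30%, and the hazard ratio h of these lesions for high HbA1c. With 1.2 for other cancers:

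HR_obs = 1.2(1 - s) + s·h.

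With h = 1.0: 1.18 (s = 0.1), 1.16 (s = 0.2), 1.14 (s = 0.3).

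**3. Information gained or lost by exclusion.** Ratio, excluding over including:

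(1 - s)(ln 1.2)² / (ln HR_obs)².

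For s = 0.2 and h = 1.0: 0.8 × 0.03324 / 0.02203 = 1.21.

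**4. Power.** Φ(√(D × 0.99 × 0.13 × 0.87) × ln HR - 1.960), where D is the number of events. Counting the lesions uses all D first events and HR_obs; excluding them uses D(1 - s) events and 1.2. Example with D = 779, s = 0.2: counted, 9.339 × 0.1484 - 1.960 = -0.574, so 28%; excluded, 8.353 × 0.1823 - 1.960 = -0.437, so 33%.

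| s (h = 1.0) | HR_obs | Information ratio | Power, 779 first events: counted / excluded | Power, about 2,109 first events: counted / excluded |
|---|---|---|---|---|
| 0.1 | 1.18 | 1.09 | 34% / 37% | 72% / 76% |
| 0.2 | 1.16 | 1.21 | 28% / 33% | 63% / 71% |
| 0.3 | 1.14 | 1.36 | 23% / 30% | 52% / 65% |

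The excluded columns leave out later cancers that would be regained when follow-up continues past a skin lesion, so they understate what exclusion offers in this scenario.

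**5. Where the sign changes.** The table holds only for h = 1.0. Setting the information ratio to 1 gives ln HR_obs = √(1 - s) × ln 1.2, hence h = [1.2^√(1 - s) - 1.2(1 - s)] / s. This is 1.088, 1.086 and 1.083 for s = 0.1, 0.2 and 0.3. Below about 1.09 exclusion gains information; above it exclusion loses. At h = 1.2 there is no dilution, the ratio is 1 - s, and exclusion loses 10%, 20% or 30%.

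**The case against.** The strongest reply is that the objective in section 2 is cancer onset in general. Counting every cancer answers that question, and a narrower primary endpoint would change it. This stands: the documents do not oblige the investigators to drop these lesions from the primary event.

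A reader might infer that the lesions do dilute the association because they are unrelated to metabolic exposure. The documents do not support that. They give neither the share of such lesions nor any association with HbA1c or BMI, and the mechanisms in the introduction (inflammation, oxidative stress, DNA damage) are not limited to particular sites. Step 5 shows that the direction of the gain depends on this unknown.

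A reader might also infer that later cancers are lost to the study. They are not: section 3.6 records a second cancer with year and type, and section 3.9 analyses it. They are absent only from the primary analysis.

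Finally, section 3.9 leaves room for analysis by type, and because the type itself is recorded, melanoma could still be separated. This is partial mitigation. The analysis is optional, and one built on first cancers would not bring back a cancer that followed a skin lesion.

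**Conclusion.** The concern holds as a gap in the endpoint definition, with dilution as a conditional consequence. The truncated follow-up, the T1 visit fixed by the lesion, the transfer of later cancers to the second-cancer model and the pooled skin class follow directly from sections 3.6, 3.7 and 3.9, and need no assumption about effect size.

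The size of any dilution rests on assumptions. With a 10-30% share and a hazard ratio of exactly 1.0 for these lesions, 1.20 becomes 1.18-1.14 and exclusion raises information by 9-36%. That is a favourable case for exclusion, and the gain reverses above a hazard ratio of about 1.09. These figures therefore do not justify imposing a new primary endpoint. They do justify a prespecified second analysis, which leaves the all-cancer result intact and shows whether the choice matters.

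**What to change.** - **Section 3.7:** split the skin class into melanoma and basal/squamous skin carcinoma. Keep squamous cell carcinoma of other sites in its own site class, since that keyword is not specific to skin.
- **Sections 3.6 and 3.9:** before extraction, prespecify an analysis of the first cancer other than basal/squamous skin carcinoma. In it, such a lesion neither ends follow-up nor starts the recurrence/second-cancer clock, and T1 covariates come from the last visit before the first other cancer.
- **Primary definition:** state which of the two definitions is primary, and report both.
- **Section 3.3.2:** apply the same definition to the exclusion for a tumor before T2D. Otherwise a skin lesion before diabetes would exclude a patient while one after diabetes was disregarded.

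Cost: fewer events in the added analysis, and more extraction for patients whose first event is a skin lesion. Tumor site must be confirmed and a second T1 visit abstracted. Cancers after the first other cancer must also be collected, because section 3.6 currently plans only for recurrence and one second cancer. Deciding before abstraction avoids returning to the records.

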3.7 Data Collection

For each patient, the following variables will be extracted from the Smart Digital Clinic electronic medical record extraction system, when possible:

- Gender and age;
- Smoking habit and alcohol consumption (units per day);
- Weight and body mass index (BMI) at the first (T0) and last visit (T1);
- Date of diagnosis of T2D;
- Date of the first visit;
- Treatment for T2D at T0 and T1;
- Levels of glycated hemoglobin (HbA1c) at T0 and T1, average HbA1c, and average fasting blood glucose;
- Creatinine clearance at T0 and T1;
- Liver enzymes at T0 and T1: alanine aminotransferase (ALT) and aspartate aminotransferase (AST);
- Lipid profile at T0 and T1: low-density lipoprotein (LDL-c) and triglycerides (TG);
- Complications of T2D;
- Treatment for the cancer;
- Family history of cancers.

The diagnosis of T2D is confirmed at diabetic centers or, in some cases, by general practitioners who refer patients to specialized diabetic centers. The accuracy of the diagnosis will be confirmed by cross-referencing with the Piedmont Diabetic Registry (PDR) and involving a second person to ensure precise assessment.

Glycated hemoglobin will be considered high if its values exceed or equal 8%, indicating glycemic decompensation, while it will be considered low if it presents values below 8%.

BMI categories will be divided into underweight (BMI <18.5 kg/m²), normal weight (BMI 18.5 – 25 kg/m²), and overweight (BMI >25 kg/m²).

Regarding the treatment of T2D, participants will be categorized and grouped for statistical purposes into the following classes:

- Dietary therapy;
- Metformin/Acarbose;
- Sulfonylurea;
- Metformin + GLP1/DPP4 inhibitors (DPP4i) or only GLP1 or only DPP4i;
- Metformin + SGLT2 inhibitors (SGLT2i) or only SGLT2i;
- Basal insulin + GLP1/DPP4i +/- Metformin;
- Basal insulin +/- Metformin +/- SGLT2i;
- Basal bolus insulin;
- Basal bolus insulin +/- Metformin +/- SGLT2i.

Furthermore, complications of metabolic pathology will be extracted from the dedicated section of the program, where they are systematically recorded and organized, and their diagnosis is conducted in accordance with appropriate guidelines. These complications will be divided into the following categories: vasculopathy, neuropathy, hypertension, heart disease, renal failure, and retinopathy.

Finally, regarding cancer, treatment will be categorized into three classes: chemotherapy, surgery, and radiotherapy. Additionally, cancer types will be divided to ensure greater homogeneity among groups, including the nervous system, head and neck, thorax, gastrointestinal, gynecological, urinary tract, male genital system, skin, blood, breast, soft tissues, endocrine glands, and neuroendocrine cancers.

Such information will be collected at the diabetes diagnosis visit and the last visit before cancer onset for subjects experiencing the event, and at the last available visit for the remaining subjects.

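### The BMI and treatment classes in section 3.7 do not serve the plan's own aims, and section 3.9 does not say which HbA1c measure, or in what form, enters the Cox models

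*Combined protocol and SAP*

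**What the plan says.** **BMI.** Section 3.7 extracts weight and BMI at T0 and T1. It then states that "BMI categories will be divided into underweight" (below 18.5 kg/m²), normal weight (18.5 to 25) and overweight (above 25). There is no further division above 25.

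**Treatment.** Section 3.7 says that "participants will be categorized and grouped for statistical purposes into the following classes" and lists nine. The last two are basal bolus insulin and "Basal bolus insulin +/- Metformin +/- SGLT2i". There is no residual class.

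**HbA1c.** Section 3.7 extracts "Levels of glycated hemoglobin (HbA1c) at T0 and T1, average HbA1c, and average fasting blood glucose". The only coding rule is "Glycated hemoglobin will be considered high if its values exceed or equal 8%, indicating glycemic decompensation", with lower values called low. Section 3.8 assumes "a prevalence of subjects with high glycated hemoglobin levels of 13" per cent. Section 3.9 says that the Cox models address some risk factors, glycemic level in particular, with stepwise selection of variables.

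**Timing.** Under section 3.6 patients are "followed from the date of diagnosis of T2D until the date of the last available visit". The closing paragraph of section 3.7 says that the information is collected at the diabetes diagnosis visit and again at "the last visit before cancer onset for subjects experiencing the event, and at the last available visit for the remaining subjects".

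**The concern.** The categories in section 3.7 are the only coding rules in the plan, so an analyst will probably apply them. Three problems follow.

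- **BMI.** If the classes are used, overweight and obese patients share one estimate, and the plan cannot deliver the statement about obesity that section 4 promises.
- **Treatment.** A patient on basal bolus insulin alone can go into either of two classes, and a patient on an unlisted combination goes nowhere. Someone must then allocate these patients by a rule that is not written down. The therapy description under secondary objective 1, and any model that uses the classes, would depend on that rule.
- **HbA1c.** The measure and form of the exposure on which the study is sized can be settled after the data are seen. Some of the available choices would also bring information from later in follow-up into a model that starts at diagnosis.

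**Working it through.** This is a question of specification, so the check sets the sections side by side and counts. The event count in section 3.8 plays no part in it.

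**1. BMI classes against the aims.** The classes are below 18.5, 18.5 to 25, and above 25. They cover every value, but no boundary lies above 25. The Introduction treats obesity as one of the most important elements shared by diabetes and cancer, and section 4 names it among the factors whose role is to be defined. No contrast between these three classes separates obese from overweight patients. Numeric BMI is on the extraction list, so the information exists. Section 3.9 does not say whether BMI enters the models as a number or as classes.

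**2. Treatment classes: overlap.** In "Basal bolus insulin +/- Metformin +/- SGLT2i" each added drug is optional. With both absent, what remains is basal bolus insulin alone, which is also the preceding class. One regimen therefore has two classes.

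**3. Treatment classes: gaps.** Take the five non-insulin groups in the list: metformin, acarbose, sulfonylurea, GLP1/DPP4i and SGLT2i. The number of pairs is 5 × 4 / 2 = 10. The list places metformin + GLP1/DPP4i and metformin + SGLT2i. It also places metformin + acarbose if the slash in that label allows both drugs. The count then depends on two labels:

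| Sulfonylurea class | Slash in Metformin/Acarbose | Pairs placed | Pairs without a class |
|---|---|---|---|
| alone only | either or both | 3 | 10 − 3 = 7 |
| alone only | either, not both | 2 | 10 − 2 = 8 |
| includes combinations | either or both | 3 + 4 = 7 | 10 − 7 = 3 |
| includes combinations | either, not both | 2 + 4 = 6 | 10 − 6 = 4 |

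The added 4 are the pairs of sulfonylurea with each of the other four groups. Among insulin regimens, basal bolus plus GLP1/DPP4i has no class under any of these readings. Basal insulin plus sulfonylurea has none unless the sulfonylurea class also takes in insulin combinations. These are counts of regimens, not of patients.

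**4. HbA1c form.** Section 3.7 defines high and low, and section 3.8 gives a prevalence of high values together with a hazard ratio. Together they imply a binary term at 8%. Section 3.9 does not adopt it, and section 3.8 does not say to which HbA1c measure the 13% refers.

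**5. HbA1c timing.** Time zero is the diagnosis of T2D. T1 is taken at the last visit before cancer in cases and at the last available visit in others, so it is known only after time zero and its date depends on the outcome. The average also needs later values. Either one, entered as a fixed covariate from diagnosis, would use future information. Section 3.9 mentions no time-dependent covariates, and its reference to variables measured at diagnosis concerns the linear regressions only.

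**6. Is T0 time zero?** The variable list in section 3.7 calls T0 the first visit and lists the date of diagnosis and the date of first visit separately. The same section says that some diagnoses are made by general practitioners who then refer. Its closing paragraph speaks of the diabetes diagnosis visit, and section 3.3 describes patients seen for a first diagnosis. The documents do not settle whether the two dates coincide.

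**7. Selection.** Stepwise selection is applied with no list of candidates or forced variables, so HbA1c could drop out of the final model although the study is sized on it.

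**The case against.** The strongest reply is that the HbA1c exposure is less open than it looks. Sections 3.7 and 3.8 together describe a binary variable at 8%, and the missing timepoint is a detail that a statistician would fill sensibly. Most of this stands. A reader might infer that the exposure is undefined altogether, or that the plan intends to use T1 or the average in the Cox model. The documents support neither. What remains is that no section names the measure, and nothing rules out the choices that look ahead.

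A reader might also infer that the 8% cut is itself an error that wastes power. The documents do not support that either. They give no HbA1c distribution and no shape for the relation with risk. A numeric term gains power if risk is log-linear in HbA1c and loses power if risk steps up at 8%.

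On BMI, the reply is that the classes may serve only for tables while the models use the number. That is possible, but section 3.9 does not say so, and the tables would still hide obesity.

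On treatment, the reply is that the gaps are theoretical combinations, and that the sulfonylurea class may be meant to include combinations. The number of affected patients is indeed unknown, and the broader reading is possible. It still leaves 3 or 4 pairs without a class, and it does not touch the basal bolus overlap.

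**Conclusion.** The point holds, most firmly for the two coding rules that fail when followed as written. The BMI classes cannot show obesity separately, against the plan's stated aim. The treatment classes give one regimen two places and several regimens none. The HbA1c part is weaker: a binary term at 8% is implied, and what is missing is its statement in section 3.9, together with the measure and timepoint.

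The size is known only as a count of regimens: one fits two classes, and 3 to 8 of 10 non-insulin pairs fit none, depending on how two labels are read. The documents do not allow an estimate of patients affected, of bias or of power. None of this stops the study, but it should be settled before the data are analysed. A reader might conclude that numeric HbA1c ought to replace the binary term as the primary form. That does not follow, because the better choice depends on a dose-response shape that the documents do not give.

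**What to change.** **BMI.** State in section 3.9 that BMI at T0 enters the Cox models as a number. In the tables, split the class above 25 so that obesity appears separately, for example at 30 kg/m² (a conventional cut, not in the documents). Cost: one more category or model term.

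**Treatment.** Merge the two basal bolus classes or make them mutually exclusive. State whether Metformin/Acarbose means either or both, and whether the sulfonylurea class includes combinations. Add a class for other combinations. Cost: a short coding rule, plus a mixed residual class whose size is not yet known.

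**HbA1c.** In section 3.9:
- Name the measure and the form.
- Use the value at the start of follow-up for the fixed-covariate Cox model.
- Reconcile the first visit with the diabetes diagnosis visit in section 3.7, so that this value is defined.
- Force HbA1c into the model instead of leaving it to stepwise selection.
- Report both the binary and the numeric term, and state in advance which is primary and which is supporting. The choice is the investigators'.
- State in section 3.8 to which HbA1c measure the 13% refers.

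Cost: mostly wording, since numeric HbA1c at T0 is already on the extraction list. A baseline value ignores later glycemic control and may be missing for some patients, because section 3.7 collects variables only where possible. If the numeric form is made primary, section 3.8 must be restated with an SD and a hazard ratio per unit, which the documents do not give.

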Finally, even diabetes drugs could be implicated. One extensively studied drug is metformin, which has shown potential as an antineoplastic agent in diabetic subjects, unlike exogenous insulin, which seems to act as a growth factor potentially implicated in cancer proliferation. (11)

All these common metabolic processes, as well as others, highlight the importance of carefully characterizing the population of diabetic patients also affected by cancer in order to understand the associated risk factors. As cancer represents a complication of diabetes, this study underscores the primary objective, which is to emphasize the necessity for tailored prevention strategies in clinical settings. These strategies aim to address specific diabetes-related risk factors that potentially contribute to cancer onset.

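### At least five of the nine diabetes-treatment classes pool metformin users with non-users, so the classes cannot cleanly isolate metformin or adjust the insulin association for it

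*Combined protocol and SAP*

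**What the plan says.** Section 3.7 (Data Collection) lists diabetes treatment at T0 and T1 among the variables to be extracted where possible, and states that "participants will be categorized and grouped for statistical purposes into the following classes". Nine classes follow. Some join a combination and a single agent by definition, such as "Metformin + GLP1/DPP4 inhibitors (DPP4i) or only GLP1 or only DPP4i" and "Metformin + SGLT2 inhibitors (SGLT2i) or only SGLT2i". Others make metformin optional, such as "Basal insulin +/- Metformin +/- SGLT2i".

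The Introduction sets two drugs against each other: "One extensively studied drug is metformin, which has shown potential as an antineoplastic agent in diabetic subjects, unlike exogenous insulin", the latter being described as a possible growth factor for tumours.

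Section 2 (Objectives) has a general primary objective, to find risk factors for a first cancer, and names no drug effect. First-line therapy appears only in the descriptive secondary objective. Section 3.9 (Statistical Analysis) singles out glycemic level as the exposure of interest, leaves the other candidates unnamed, selects variables stepwise, and does not say how treatment is coded. Neither 3.7 nor 3.9 provides a separate metformin or insulin variable.

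**The concern.** A treatment variable can inform a search for risk factors only if its levels separate the exposures of interest. Here most levels do not separate the one oral drug that the Introduction singles out, and three of the four insulin levels mix it with the drug to which it is contrasted. Making the classes mutually exclusive and complete would not cure this, because the pooling lies inside the classes.

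Three things are at stake:

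- A hazard ratio for an insulin class would depend on an unreported share of metformin co-users, so a weak result could reflect the grouping as well as the drug.
- A diluted class variable may be dropped by the stepwise procedure and then be read as showing that treatment is not a risk factor.
- Adjustment of the HbA1c association for treatment would be incomplete with respect to metformin.

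The same coding would carry over to the recurrence and second-cancer models, and to the analysis of time to cancer against characteristics at diagnosis.

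**Working it through.** The plan gives no figure on this point. Its one computed figure, the number of cancer cases in section 3.8, concerns HbA1c and is not an input here.

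**Step 1. Metformin status in each class (section 3.7, in the order listed).**

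| Class | Metformin status |
|---|---|
| 1. "Dietary therapy" | None |
| 2. "Metformin/Acarbose" | Mixed if the slash means *or*; all users if it means *and* |
| 3. "Sulfonylurea" | Not named; no class is listed for sulfonylurea plus metformin |
| 4. "Metformin + GLP1/DPP4 inhibitors (DPP4i) or only GLP1 or only DPP4i" | Mixed, explicit |
| 5. "Metformin + SGLT2 inhibitors (SGLT2i) or only SGLT2i" | Mixed, explicit |
| 6. Basal insulin with GLP1 or DPP4i, metformin optional | Mixed, explicit |
| 7. "Basal insulin +/- Metformin +/- SGLT2i" | Mixed, explicit |
| 8. Basal bolus insulin, no other drug listed | None as written, but these patients also fit class 9 |
| 9. Basal bolus insulin, metformin and SGLT2i optional | Mixed, explicit |

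Classes 4, 5, 6, 7 and 9 are explicitly mixed: 5 of 9. Reading the slash in class 2 as *or*, as it appears to be used for GLP1/DPP4 in the same list, makes it 6 of 9. Of the four insulin classes (6 to 9), three are mixed (6, 7 and 9).

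**Step 2. What the classes can still give.**

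- Metformin: class 2 against class 1 is a contrast diluted by patients on acarbose alone (slash as *or*), or a contrast of metformin with acarbose against diet (slash as *and*). Neither uses the metformin users in the five explicitly mixed classes. A yes/no metformin variable cannot be rebuilt from the classes.
- Insulin: classes 6 to 9 against classes 1 to 5 gives any insulin versus none. Metformin cannot be entered beside it.

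**Step 3. Illustration of size. All hazard ratios and shares are assumed; none is in the documents.** Let HI be the insulin hazard ratio, HM the metformin hazard ratio (effects multiplicative), and f the share of an insulin class also on metformin. Against a reference on neither drug, approximately:

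class HR = HI × [(1 − f) + f × HM], with HI = 1.2.

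| HM | f = 0% | 25% | 50% | 75% | 100% |
|---|---|---|---|---|---|
| 0.7 | 1.20 | 1.11 | 1.02 | 0.93 | 0.84 |
| 0.8 | 1.20 | 1.14 | 1.08 | 1.02 | 0.96 |
| 0.9 | 1.20 | 1.17 | 1.14 | 1.11 | 1.08 |

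For example, with HM = 0.8 and f = 50%: 1.2 × (0.5 + 0.5 × 0.8) = 1.08. The class HR reaches 1 when f = (1 − 1/1.2)/(1 − HM) = 0.167/(1 − HM). That is 0.56 for HM = 0.7 and 0.83 for HM = 0.8. For HM = 0.9 it is 1.67, which cannot occur.

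**Step 4. Any insulin versus none.** The comparison group also contains metformin users, at a share f0. Write f1 for the share in the insulin group. The apparent ratio is then 1.2 × [(1 − f1) + f1 × HM]/[(1 − f0) + f0 × HM]. With HM = 0.8:

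- equal shares: 1.20, no distortion;
- f1 = 75%, f0 = 25%: 1.2 × 0.85/0.95 = 1.07;
- f1 = 25%, f0 = 75%: 1.2 × 0.95/0.85 = 1.34.

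The distortion can therefore go either way or be absent.

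**The case against.** The strongest reply is that the plan never undertakes to estimate a metformin effect. The objectives name no drug, the study is sized on HbA1c, and metformin as a cancer-relevant drug appears in one hedged background sentence. Section 3.9 does not state that the nine classes enter the Cox models, and regimen classes are a defensible way to describe treatment intensity. All of this stands. It limits the point to treatment as a candidate risk factor and to adjustment, and makes it conditional on the classes being the model variable. That condition is the natural reading of section 3.7, since no other treatment coding is offered.

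A reader might infer several stronger things that the documents do not support:

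- *The metformin hazard ratio is not estimable at all.* Class 2 against diet gives a diluted contrast. What is missing is a clean one that needs no assumption about the mix.
- *Six of nine classes are mixed.* This depends on how one slash is read; five is the number that the text fixes.
- *The insulin result is uninterpretable.* Any insulin versus none remains available; what is lost is its adjustment for metformin.
- *The grouping alone would erase or reverse an insulin signal.* This depends on the assumed metformin effect as well as on the mix. At a metformin hazard ratio of 0.9 it does not happen at any mix. At 0.8 it needs more than about 83% co-use, and at 100% the class is no longer mixed.
- *The HbA1c hazard ratio is materially biased.* The classes still adjust for regimen and partly for metformin, and nothing in the documents sizes the remainder.

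**Conclusion.** The point holds with limits. At least five of the nine classes, and three of the four insulin classes, pool metformin users with non-users. If these classes are the treatment variable in the Cox models, the metformin association cannot be cleanly isolated, and the insulin association cannot be adjusted for metformin. This is a poor match to an Introduction that presents the two drugs as contrasting.

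The size cannot be derived from the documents. On the assumed values, an insulin class with half its patients on metformin shows 1.02 to 1.14 in place of 1.20, against a reference on neither drug. This assumes multiplicative effects and no confounding by the reason for treatment choice. For the HbA1c association the consequence is incomplete adjustment of unknown size. The change is worth making because it is cheap and gives a better coding for finding treatment-related risk factors. It is not a condition for the HbA1c analysis to go ahead.

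**What to change.** In section 3.7, state that drug-level detail will be kept, where the record gives it, before the treatment field is collapsed into classes. In section 3.9, state that the treatment covariates in the Cox models are yes/no indicators for metformin and insulin at T0, entered together so that each is adjusted for the other. Add sulfonylurea, acarbose, GLP1/DPP4i and SGLT2i where counts allow. Keep the nine classes for the descriptive table and, if wanted, for a secondary comparison of regimens. State also whether the slash in class 2 means either drug or both, and resolve the overlap between the two basal bolus classes, so that the retained classes can be reproduced.

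The cost is a recode of a field that is to be extracted anyway, and a sentence or two in each section. It depends on the record holding drug-level treatment. Sparse agents may need merging. Indicators taken at one visit do not capture duration, switching or later starts, so the metformin and insulin hazard ratios should be reported as associations with treatment at T0 only.
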